## 2) Objectives

**Primary Objective:** To culturally tailor a technology-based individualized adherence intervention for Black and Latino patients with uncontrolled HTN or T2DM, who are non-adherent to their medications, and determine its acceptability.

**Secondary Objective:** To assess the feasibility of the methods and procedures to implement the individualized adherence intervention within a primary care practice in New York City.

**Tertiary Objectives:** To compare the efficacy of a tailored adherence intervention to a single patient education (PE) session on:

- a. Change in medication adherence at 3 months.
- b. Blood pressure (BP) reduction at 3 months.
- c. HbA1c reduction at 3 months.

**Hypotheses:** Among 40 Latino and Black patients with uncontrolled hypertension (HTN) or type 2 diabetes those randomized to the intervention, compared to those randomized to PE, will:

- a. Exhibit higher rate of adherence to their antihypertensive or anti-diabetic medications at 3 months.
- b. Exhibit a greater reduction in systolic and diastolic BP at 3 months.
- c. Exhibit a greater reduction in HbA1c at 3 months.

## 3) Background

Despite advances in treatments for cardiovascular-related diseases (CVD; e.g., hypertension [HTN], type II diabetes mellitus [T2DM]) over the past three decades, CVD remains the leading cause of death in adults. T2DM affects 29.1 million people in the U.S., and the incidence is growing rapidly. (Center for Disease Control and Prevention, 2014) CVD incidence is nearly three-fold higher in patients with T2DM. (Fox et al., 2015) Blacks have the greatest burden of T2DM in the U.S., with nearly 5 million Black adults having diabetes. (Blackwell DL, 2014) As compared to Whites, Blacks and Latinos are 80% more likely to be diagnosed with diabetes and more than three times as likely to experience complications such as end stage renal disease, blindness, and lower extremity amputations. (Blackwell DL, 2014) Uncontrolled HTN, a leading risk factor for CVD, is the single most important predictor of subsequent cardiovascular morbidity and mortality among patients with T2DM. HTN occurs in more than 50% of patients with T2DM, and T2DM patients have a 1.5 to 3-fold risk for HTN. Latinos are the fastest growing ethnic group in the US with a growth rate of 43% compared to 23% among whites over the past decade. (Ennis SR, Ríos-Vargas M, & Albert NG, 2011) This increase is four times the nation's 9.7% growth rate, and accounts for more than half of the total U.S. population increase of 27.3 million during this period. (Ennis SR et al., 2011) This growth is

accompanied by a significant increase in cardiovascular disease (CVD)-related morbidity and mortality.(Davidson et al., 2007) Despite increasing trends in the awareness and treatment of hypertension (HTN) among all groups, Latinos have the lowest blood pressure (BP) and blood glucose control rates in the US.(Yoon, Ostchega, & Louis) While barriers to optimal HTN control, such as poor access and low awareness, explain some of the disparities in disease control between Latinos and whites, BP control rates still remain lower among Latinos who receive treatment compared to whites.(Liu, Liu, Tsilimingras, & Schiffrin). Blacks in particular, have the highest prevalence of HTN in the US with approximately 42% affected, an estimate that is nearly 50% higher than the prevalence rates in Whites. These differences become even more striking after considering the significantly earlier onset of HTN and higher rates of cardiovascular disease, diabetes, stroke, and end stage renal disease in Blacks compared to Whites. Poorer medication adherence among Blacks and Latinos may explain the disproportionately lower rates of BP control in these patient populations when compared to Whites. Nearly 60% of Blacks with T2DM have poor glucose control and poor blood pressure (BP) control.(McWilliams, Meara, Zaslavsky, & Ayanian, 2009) Poor medication adherence is a major contributor to inadequate BP control, and is associated with 125,000 deaths annually.(Morris & Schulz, 1992) Despite over 30 years of research dedicated to understanding adherence behaviors in hypertensive patients, data in minority patients is scant. More importantly, translation of adherence interventions to community-based primary care practices where majority of minority patients receive care is non-existent. Thus, the development of tailored interventions targeted at improving medication adherence in this high-risk population is needed to address the racial/ethnic disparities in BP and glucose control. To address this gap, this proof of concept study will assess the feasibility and compare the efficacy of a tailored technology-based adherence intervention (TAI) vs. a single patient education session (PE) on medication adherence among 40 Latino and Black patients with uncontrolled HTN or type 2 diabetes. Findings from this pilot study will lay the foundation for developing a larger, multi-site randomized controlled trial to improve medication adherence and blood pressure control among Latinos and Blacks.

#### **4) Inclusion and Exclusion Criteria**

##### **Screening Procedures:**

Potentially eligible patients will be identified using two methods:

1. An RA will work with clinic physicians at the ambulatory care center to identify potentially eligible patients. The RA will screen the EHRs of patients with upcoming clinic appointments to determine initial eligibility (i.e., high blood pressure/type 2 diabetes diagnosis and date, race/ethnicity) and will review the list of potentially eligible patients with clinic physicians.
2. By asking primary care providers (PCP) to refer patients who meet the eligibility criteria to a research assistant (RA) who will then conduct an onsite screening and consent visit. Once a patient is identified who fulfills the inclusion criteria, a letter, signed

## PROTOCOL TITLE: Tailored Approaches to Improve Medication Adherence

by the referring provider, will be sent to the patient, explaining the study and providing a telephone number, for him/her to call if s/he is interested in participating. If the patient gets in contact with study staff, the study staff will provide more information about the study (via telephone or in a dedicated space in the clinic).

### **Eligibility Criteria:**

Potentially eligible patients must (a) have uncontrolled HTN defined as BP $\geq$ 140/90 mmHg on at least two consecutive visits in the past year (or BP $\geq$ 130/80 for patients with diabetes and/or kidney disease) or uncontrolled T2DM defined as A1c $>$ 7%(Fox et al., 2015) on at least two consecutive visits in the past year; (b) have been prescribed at least one antihypertensive or oral anti-diabetic medication; and (c) self-identify as Latino or African American/Black and be  $\geq$  18 years of age.

Patients will be excluded if they (a) refuse or are unable to provide informed consent; (b) currently participate in another HTN or type 2 diabetes study; (c) have significant psychiatric comorbidity (determined by EMR and confirmed by the patient's PCP); or (d) plan to discontinue care at the clinic within the next 3 months.

Vulnerable populations including adults unable to provide informed consent, pregnant women, and prisoners will be excluded from this study.

### **5) Number of Subjects**

A total of 40 subjects will be recruited for this study.

### **6) Recruitment Methods**

Potentially eligible subjects will be recruited in four ways:

1. First, after identifying potentially eligible patients via the EHR review, the physician will briefly introduce the study to any patient they deem suitable. Those patients who are interested and give either verbal consent to the physician will speak to the RA, who will provide additional information and a study brochure. Patients who remain interested may complete informed consent and the first screening visit at that time, or may be scheduled for a screening visit at a later date.

The information obtained from the EHR for pre-screening will be: race/ethnicity, high blood pressure and/or type 2 diabetes diagnosis and date, and MRN. Patients found to be initially eligible based on this information will be presented to Bellevue physicians to determine suitability for the study. If the potential participant is not deemed suitable for the study by the physician, does not keep their screening appointment, or does not agree to participate once approached, all PHI collected from these subjects will be discarded and not retained for study purposes.

PROTOCOL TITLE: Tailored Approaches to Improve Medication Adherence

2. Second, healthcare providers will continue to refer patients during the trial. Healthcare providers as well as nurses, and patient care assistants (PCAs) will be given a card which gives the inclusion criteria; the provider/nurse/PCA will explain to potential participants that there is a study in which s/he might be interested in participating. If the patient expresses interest, the healthcare providers, nurse or PCA will give the patient a card with the study staffs' telephone number. The same follow-up procedures will be used as noted in method 1.
  
3. Third, to maximize our reach, a random sample of patients who participated in [name] IRB approved project #11-0053 and indicated on the main project consent form that they are willing to be re-contacted in the future will be contacted by [name]. In order to contact these patients, the following information will be obtained from [name] trial: Name, mailing address, and phone number. This information will be used to contact the patients via a postal letter and then by a phone call. The letter will include a brief description of the project and the reason why they are being contacted to participate. It will also provide information about how to get in touch with [name] to schedule an in person visit and it will inform participants that [name] will be contacting them soon via a phone call. During the call the [name] will explain that the purpose of the project and the patient's responsibilities. If the patient expresses interest in completing the survey and agrees to participate at this point, s/he will be scheduled for the consent visit.

In order to randomly select patients to receive an interest letter, each and patient that completed project #11-0053 will be assigned a number. Using a random number table, three patients will be chosen to receive a letter. We will then use the following procedures for each patient: If the first patient chosen refuses to participate when called, research personnel will approach the second person chosen, and so on until a participant agrees to the project or the list is exhausted. This process will continue until all potential patients are contacted and invited to participate in the study.

4. Fourth, flyers will be hung in the clinic waiting rooms. The flyer will include a brief description of the project and information about how to get in touch with [name] to schedule an in person visit, if the patient is interested in obtaining more information or being screened for the study.

## **7) Study Timelines**

The duration of participation for each study subject is three months. Based on our previous studies with this patient population, we estimate that we will recruit 6 patients per month to participate in the study. Thus, it is anticipated that 3.5

## PROTOCOL TITLE: Tailored Approaches to Improve Medication Adherence

months will be needed to recruit all study subjects. The estimated date of study completion is 24 months.

### **8) Study Endpoints**

The primary objective will be accomplished through 10 individual key informant interviews with Black patients with uncontrolled HTN or type 2 diabetes. The interviews will elicit ideas to improve medication adherence, examine Black and Latino patients' use of technology, attitudes toward mHealth interventions, and elicit their feedback of intervention prototype designs including the cultural relevance of the program content, acceptability of the format and mode of delivery.

The secondary objective, which will evaluate feasibility of the intervention will be assessed through an ongoing formative evaluation to identify barriers and facilitators to implementation in a primary care setting, which will be used to inform necessary protocol modifications and continuously refine the methods.

The tertiary objective of medication adherence to prescribed antihypertensive or anti-diabetic medications at 3 months will be assessed with the well-validated 8-item self-report Morisky Medication Adherence Scale (described in Section 9).

The tertiary outcome of reduction in blood pressure (BP) from baseline to 3 months. BP will be assessed with a validated automated BP monitor (WatchBP) based on American Heart Association guidelines.

The tertiary outcomes of reduction in HbA1c from baseline to 3 months with an automated validated point-of-care device based on American Diabetes Association guidelines.

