**Tailored Adherence Intervention (TAI) group:** Following the completion of the study measures, patients randomized to the TAI group will complete the technology-delivered tailoring survey and engage with intervention strategies that are matched to individualized adherence profile identified in the survey. After completing the program, the patients will be thanked, given reimbursement to defray transportation costs (\$20), and scheduled for the 3 month study visit.

**Three-Month (post randomization) Study Visit will be the same for both groups:** Patients will have 3 BP measurements taken using the automated BP device, have their HbA1c measured with the point-of-care device, and complete the self-report measures with the assistance of the RA in a private room in the clinic. . In order to facilitate completion of the 3-month follow-up visit, patients will receive a reminder post card containing the study contact information.

**Exit Interviews:** To evaluate the effectiveness and relevance of the intervention to the patients, we will conduct individual exit interviews with 10 randomly selected intervention participants. The interview questions will ask participants' opinion on the intervention approach. The interviews will help us determine which intervention components are most effective in assisting participants in taking their medication as prescribed, and which components of the intervention can be improved to make it more relevant to the target population. Patients will receive \$10 for completing the interviews.

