## 10) Data Management

**Sample size calculation:** For the primary aim, we will recruit 10 patients of the target patient population to culturally tailor the technology-based adherence intervention to ensure saturation of themes will be reached. For the secondary and tertiary aims, we will enroll 20 patients per group (40 total); allowing for a 15% rate of attrition that will yield a final sample of approximately 15 patients per group who complete the study. Given the paucity of studies on medication adherence among Latinos and Blacks with hypertension, there is not sufficient data for power estimation. However, this pilot study will give us the opportunity to calculate the power needed to carry out a larger trial.

**Randomization and blinding:** To ensure a roughly equal assignment of patients to the two groups, we will use a block size of 4 with a permutation of 2 patients randomly assigned to each group, with the investigators blind to the permutation. Following CONSORT guidelines, (Bellg et al., 2004; Resnick et al., 2005) the randomization sequence will be generated by the statistician and kept in sealed opaque envelopes in a locked cabinet away from the study site. Once the RA has identified a patient that has met eligibility criteria and provided consent, the research assistant (RA) will call the study statistician for the patient's group assignment. All randomized subjects will be included in the analyses using intent-to-treat strategies. As is true for most behavioral interventions, the patient cannot be blinded to the group assignment. (Bellg et al., 2004) However, the RA conducting the data collection will be blinded to the patients' group assignments and a separate RA will be used for data collection

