**Data Storage and Confidentiality:** PHI obtained during pre-screening (with a waiver of authorization) will not be retained unless the subject provides informed consent. Any PHI collected after informed consent will be entered as part of the data set. To ensure confidentiality, baseline and 3 month data will be associated with an individual participant only by an assigned identification number, the code for which will be kept in a password protected file accessible only by the study team. Procedures have been centrally developed to ensure the confidentiality of information, such as encrypting all data, storing all hard copies of study related data in locked cabinets, password protecting all electronic files, ensuring that participant information is not identified with participant names, and that analyses are conducted and reported by group rather than by individual participants. All data will be maintained on a secure, physical and password-protected central computer server. Prior to inclusion in any data set (internal and external), data will be stripped of all identifying information. Access to the HIPAA-compliant database will be controlled by passwords, which are encrypted and required to meet standard security requirements.

**Procedures for audiotapes:** In this study, audio recordings of the semi-structured interviews will be completed to identify themes related to barriers and facilitators of medication adherence. These data will be used to tailor the adherence intervention program. All recordings will be conducted in a private dedicated room at the primary care clinic. Permission and signed informed consent will be sought from participants to complete the audiotape interviews. All participants will be informed that audiotaping is optional and refusal to sign the informed consent will not limit their participation in the study. In addition, participants have the right to review the tapes and can request for withdraw of the tapes at any time after giving consent without penalty. In the event that a participant requests withdrawing tapes, the tapes will be erased and destroyed. Withdrawing tapes from the study will not impact the care that patient receives or provider delivers at the Ambulatory Care Practice. To ensure confidentiality, all tapes will be assigned a unique study identifier and will be stored in locked file cabinets in a

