Statistical Analytic Plan
Tailored Approaches to Improve Medication Adherence
NCT01643473
05/10/2018

Analysis of the qualitative data: [name] and a trained research assistant conducted the qualitative analysis of the audiotaped interview data. Transcripts of the interviews were uploaded to the Atlas.ti program in order to code the data and facilitate content analysis. The transcripts were individually reviewed and analyzed using the grounded theory constant comparison method. Specifically, transcripts were coded line-by-line using open coding (comparing and categorizing data to generate concepts); axial coding (reorganizing data into categories based on relationships within and between these categories); and selective coding (identifying and describing the central themes to generate a conceptual framework) according to issues related to medication-taking (e.g., side effects, cost, forgetfulness). Once the transcripts were independently coded, the research team met to discuss the coding and resolve any discrepancies.

Analysis of study feasibility: We assessed reach of the intervention by examining the ratio of eligible participants invited to participate vs. those that enroll in the study. We also collected data on patients' age and gender to determine if there are any differences between eligible participants that do not enroll vs. enrollees. Independent t-tests and the chi-square statistic were used to determine if there are any significant differences between the groups. Reasons for not enrolling in the program were also documented. In addition to these outcomes, exit interviews were conducted with a subsample of 12 participants to assess acceptability and satisfaction with the program.

Analysis of exploratory outcomes: To test the exploratory aim, we conducted separate differences in differences estimations for each of the outcome measures (i.e., adherence, BP HbA1c) whereby pre-intervention values are subtracted from post-intervention values, and change amounts by study group are compared using t tests. We also conducted linear regression models to examine whether the average baseline scores were significantly different from the average scores at 3 months, when, controlling for baseline levels of the outcome measure (i.e., adherence, BP HbA1c), age, gender socioeconomic status (SES), insurance status and number of medications

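### The endpoint section names only Black patients for the ten tailoring interviews, contradicting the Black and Latino primary objective, and no other section secures Latino input

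*Protocol*

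**What the plan says.** The primary objective (Protocol, section 2) is "To culturally tailor a technology-based individualized adherence intervention for Black and Latino patients with uncontrolled HTN or T2DM", together with determining whether the intervention is acceptable.

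Section 8 (Study Endpoints) explains how that objective will be met: through "10 individual key informant interviews with Black patients with uncontrolled HTN or type 2 diabetes". Its next sentence says the same interviews will, among other things, "examine Black and Latino patients' use of technology, attitudes toward mHealth interventions" and collect feedback on the prototypes, including their cultural relevance.

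Section 10 (Sample size calculation) describes the interview sample differently: "we will recruit 10 patients of the target patient population to culturally tailor the technology-based adherence intervention". It justifies the number by saturation of themes. The eligibility criteria in section 4 require that patients "self-identify as Latino or African American/Black". Section 10 (Procedures for audiotapes) says of the recorded interviews: "These data will be used to tailor the adherence intervention program".

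The SAP describes how the interviews were coded but not who was interviewed.

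**The concern.** Section 8 is the only place that states the race or ethnicity of the interviewees, and it does so in the sentence that defines how the primary objective is achieved. That sentence names one of the two groups for whom the intervention is to be tailored.

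The study's main product is a culturally tailored programme, and section 21 admits both English- and Spanish-speaking Latino patients. If interviewers recruited from the section 8 sentence, the programme could be called culturally relevant and acceptable to Latino patients with no assurance that any Latino patient had been consulted before it was built. A reader of the final report could not tell from the protocol or the SAP whether this happened.

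**Working it through.** No statistical formula lies behind the number of interviews. It is 10 in both section 8 and section 10, so the count agrees, and the question is only who the ten are.

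**Step 1: the passages side by side.**

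| Place | What it describes | Group named |
|---|---|---|
| Protocol 2, primary objective | Whom the intervention is tailored for | Black and Latino |
| Protocol 8, first sentence on the primary objective | Who is interviewed | Black only |
| Protocol 8, next sentence | What the interviews examine | Black and Latino |
| Protocol 10, sample size | Who is recruited for tailoring | Target population, not restricted further |
| Protocol 4, eligibility | Definition of that population | Latino or African American/Black |
| SAP, qualitative analysis | How transcripts are coded | Not stated |

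One entry differs from the rest. It also conflicts with the sentence that follows it, because interviews confined to Black patients cannot report on Latino patients' technology use, except through interviewees who are both Black and Latino.

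**Step 2: does any other section secure Latino input to the tailoring?**

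- *Section 10, sample size.* It removes the restriction but sets no composition. Any number of Latino interviewees from 0 to 10 fits its wording.
- *Exit interviews, section 9.* These are "individual exit interviews with 10 randomly selected intervention participants", with no ethnic restriction. They take place after the programme has been delivered, so they cannot inform its initial tailoring, and random selection fixes no Latino share.
- *SAP.* It reports that "Transcripts of the interviews were uploaded to the Atlas.ti program in order to code the data and facilitate content analysis". It gives no composition of the interview sample.

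So Latino input is allowed on the broader reading and guaranteed on none.

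**Step 3: how many trial patients could be affected.**

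Inputs: 20 patients per group (section 10), and a Latino share of 30% to 70%, which is my assumption because the documents give no split. Only the intervention arm counts. The education arm receives a session on unrelated topics (section 9), not the tailored adherence content.

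Expected Latino patients in the intervention arm = 20 × share:

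- 20 × 0.30 = 6
- 20 × 0.70 = 14

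These are expected counts. The randomisation described in section 10 is blocked but not stratified by ethnicity, so the actual number could differ.

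**The case against.** The best defence is that this is a dropped phrase. The next sentence of section 8 speaks of both groups, and the recruitment statement in section 10 refers to the whole target population. Nothing in the protocol ranks the section 8 sentence above section 10. This stands as far as intent goes: an omitted *and Latino* is a plausible explanation. It does not remove the contradiction, and the corrected wording would still leave the composition of the ten unstated.

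A reader might go further and infer that Latino tailoring rests on no Latino input. The documents do not support that. It follows only if one sentence is read apart from its neighbours. Even then it is not strictly zero, because the eligibility criteria do not make Black and Latino mutually exclusive.

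It can also be said that Latino views enter elsewhere. Exit interviews address acceptability (the SAP reports 12 of them), and each patient's own barrier scores determine the adherence profile to which that patient is assigned (section 10). Both points are fair, and they rule out saying that there would be no data on acceptability to Latino patients. Neither replaces Latino input before the programme was built.

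Lastly, the SAP, dated 05/10/2018, is written in the past tense, so the interviews appear to be complete. That stands, and it shifts the remedy from planning towards disclosure.

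**Conclusion.** The section 8 sentence is wrong as written. It contradicts the primary objective, the sentence after it and the sample size section. Followed literally, it would not secure Latino input to the cultural tailoring, and no other section does so. This part rests on the text alone.

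The size is minor to moderate. If the literal wording governed recruitment, about 6 to 14 of the 20 intervention-arm patients would receive content tailored without assured Latino input, under the assumed 30% to 70% Latino share. It would be tempting to apply that share to all 40 randomised patients, but that would count education-arm patients who never receive the tailored content.

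The documents do not settle whether the wording was a slip, or who was actually interviewed. The randomised comparison of adherence, blood pressure and HbA1c is not compromised. What is at stake is the support for the claims of cultural relevance and acceptability.

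**What to change.** 1. In Protocol section 8, add *and Latino* after *Black* in the sentence on the key informant interviews, so that it matches sections 2 and 10.
2. State the planned Black/Latino composition of the ten or, if the interviews are complete, the actual composition. The SAP's qualitative paragraph or the study report would be a suitable place.
3. If no Latino patient was interviewed, limit the cultural-tailoring and acceptability conclusions drawn from these interviews to Black patients.

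The cost is a two-word correction in the protocol and a line of reporting. The number of interviews stays at ten. A minimum number per group, or themes reported separately by group, would be a preference; nothing in the documents requires either. Section 10 justifies ten interviews by saturation in the target population as a whole, and splitting them would weaken that basis within each group.
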